### 3.6.2 Clinical Laboratory Values

The Schedule of Visits and Procedures shows the time points at which blood and urine will be collected for clinical laboratory tests. Laboratory tests should be performed under fasting conditions. Any laboratory abnormality may qualify as an AE in the Investigator's judgment. A complete list of all clinical laboratory assessments is presented in Table 2.

For subjects who participate in the optional PK portion of the study, a total of approximately 32mL (8 PK blood draws  $\times$  4mL) of blood/subject will be taken during the course of the study for the purpose of PK samples, in addition to 30mL (2 blood draws for clinical chemistry  $\times$  15mL) required for laboratory tests for all subjects.

Table 2. Clinical Laboratory Assessments

Hematology	Serum Chemistry	Urinalysis		
Hematocrit Hemoglobin Red blood cell count (RBC) Platelet count White blood cell count (WBC) (with differential)	Albumin Alkaline phosphatase Alanine transaminase (ALT) Aspartate transaminase (AST) Bilirubin- Total and Direct Blood urea nitrogen (BUN) Calcium Chloride Cholesterol- Total, HDL and LDL Creatinine Creatine phosphokinase (CPK) Gamma-glutamyl transpeptidase (GGT) Glucose Inorganic phosphorous Potassium Sodium Total protein Triglycerides Uric acid	Ketones Protein Specific gravity Glucose pH		
Other tests				
Urine drug panel for drugs of abuse (amphetamines, barbiturates, benzodiazepines, cocaine, marijuana/cannabinoids, methadone, opiates, phencyclidine, propoxyphene, and alcohol)				
Urine pregnancy test (for FOCP)				

## 3.6.3 Vital Signs, Height, and Weight Measurements

CYP2D6 enzyme activity (poor, intermediate and ultra rapid metabolizers)

Vital sign measurements (HR, blood pressure, temperature, and respiratory rate) will be obtained at all visits as designated on the Schedule of Visits and Procedures (Table 1). Blood pressure and pulse will be measured after the subject has been sitting for 5 minutes. Height and weight will be obtained at the Screening Visit and weight will be collected at all visits as designated on the Schedule of Visits and Procedures (Table 1).

# 3.6.4 Medical, Psychiatric History and Physical Examinations

Medical and psychiatric history, including smoking history, will be taken at the Screening Visit. Physical examinations will be performed at the Screening Visit and Final Visit as designated on the Schedule of Visits and Procedures (Table 1).

### 3.6.5 Electrocardiograms (ECGs)

ECGs (12-lead) will be obtained at the Screening Visit, Visit 4, and the Final Visit as designated on the Schedule of Visits and Procedures (Table 1). Additional ECGs may be performed at other times if deemed necessary.

The ECG will be recorded while the subject is resting in a supine position. The ECG will electronically measure the PR, QRS, QT, and QTc intervals, and heart rate. QTc will be reported as QTcF (QT corrected using Fridericia's method).

### 3.6.6 Prior and Concomitant Medications

For subjects who receive SM, prior and concomitant medications and therapies that are ongoing as of the date of informed consent will be recorded on the Concomitant Medication CRF. The Investigator will record all concomitant medications, including over-the-counter medications, on the Concomitant Medication CRF. The Investigator will record the AE for which the concomitant medication was administered on the AE CRF.

#### 3.7 COMPLETION/DISCONTINUATION OF SUBJECTS

Subjects will be permitted to leave the study at any time. Subjects can be withdrawn from the study in any of the following circumstances:

- SAE or an AE
- Administrative reasons (e.g., sponsor decision)
- Withdrawal of consent/assent
- If the subject becomes pregnant
- If it is in the best interest of the subject, in the opinion of the Investigator
- Termination of the study.

If a subject is prematurely discontinued from participation in the study for any reason after SM administration, the Investigator must make every effort to perform the Final Visit assessments.

### 4. DATA ANALYSIS

Tabular summaries of the data collected during the study will be presented to provide a general description of the subjects studied and an overview of the efficacy and safety results. Data from all sites will be combined in the computation of these summaries, and summaries will be presented by treatment group. All subjects randomized to SPN-812V 300mg/day group, whether they are maintained on 300mg or reduced to 150mg, will be analyzed under the SPN-812V 300mg/day group. Continuous variables will be summarized using descriptive statistics (number of subjects, mean, standard deviation [SD], median, and minimum and maximum values). Categorical (nominal) variables will be summarized using frequency tables (number and percentage of subjects in each category). If some values are missing, the percentages will sum to less than 100%.

In addition to tabular summaries, subject data listings will be provided. All data collected on eCRF and from central laboratory will be presented in data listings. Where appropriate, data will be summarized for each protocol-specified visit. Unscheduled data will be listed and included in the Last Observation Carried Forward (LOCF) analysis.

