## 7. INTRODUCTION

Viloxazine was previously marketed as an antidepressant in several European countries, since the 1970's, and is currently under development by the Sponsor as SPN-812V, for its potential utility in treating adult attention deficit hyperactivity disorder (ADHD). Viloxazine is a racemate and Supernus plans to develop the compound as such. Supernus intends to carry out this preliminary safety and proof of concept study in adult ADHD patients using an immediate release formulation that will support future development of a modified release formulation to facilitate compliance and possibly improve tolerability.

Similar to tricyclic antidepressants and atomoxetine, viloxazine is an inhibitor of the reuptake of norepinephrine, but may also enhance the release of serotonin from neuronal stores. Clinical efficacy in Major Depressive Disorder has been shown at daily doses of 300 to 600 mg. Thorough published pharmacological and clinical summaries of the product are found in the reviews of Pinder et al., 1977 and Ban et al., 1980.

Supernus development thesis is based on the current unmet medical need for effective longacting non-stimulant treatment for ADHD in adults. Viloxazine can offer a compelling alternative to the use of scheduled substances to control ADHD thus limiting patients' exposure to agents with potential for substance abuse. This Phase I/IIa study seeks to evaluate the safety and tolerability of an immediate release formulation of viloxazine given three times per day (TID) at a dose of 150 or 300mg/day in adults. A randomized, multicenter, parallel group, double-blind, placebo-controlled dose-ranging study design will be used. 50 subjects will be randomized; assuming a 20% dropout rate, it is anticipated that 40 subjects will complete the study. Subjects will be monitored regularly for safety endpoints.

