### 9.7.1.4.2. Laboratory Values

By-visit tabular summaries of the laboratory test results will be presented. For quantitative laboratory tests, both actual values and change from screening values will be summarized.

Laboratory test results will be assigned an LNH classification according to whether the value was below (L), within (N), or above (H) the laboratory parameter's reference ranges provided by the central laboratory. Within treatment comparisons will be based

on 3 by 3 tables (shift tables) that, for a particular laboratory test, compare the LNH classification at screening to the LNH classification and the Final Visit.

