### 3.2 SAMPLE SIZE CONSIDERATION

Approximately 50 subjects (approximately 25 per treatment group) will be randomized in the study. The sample size is not based on any statistical considerations, but it was judged adequate to provide safety, PK, and efficacy information for a proof-of-concept study.

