### 4.2 ANALYSIS POPULATIONS

The population of "All Screened Subjects" will contain all those subjects who entered the screening period to determine their eligibility to participate in the study.

The population of "All Randomized Subjects" will contain all those screened subjects who meet the requirements for study participation and are randomized, using a centralized randomization system, to either SPN-812V or placebo.

The "Intent-to-Treat (ITT) Population" consists of all randomized subjects who took at least one dose of SM, had baseline efficacy assessment and had at least one post-baseline efficacy assessment. The ITT population is the primary population for the efficacy analysis.

The "Restricted ITT Population" consists of all ITT population subjects with at least 1 efficacy assessment after three weeks of treatment.

The ITT and Restricted ITT populations will be analyzed according to treatment assigned. All subjects randomized to SPN-812V 300mg/day group, whether they are maintained on 300mg or reduced to 150mg, will be analyzed under the SPN-812V 300mg/day group.

The "Safety Population" consists of all randomized subjects who receive at least 1 dose of SM.

The PK population consists of all safety subjects who consented to participate in the optional PK sub study and had at least one evaluable (non-BLQ) PK sample drawn.

The safety and PK populations are based on actual treatment received.

Table 14.1.2 provides these analysis populations for all randomized subjects.

Listing 16.2.2 provides inclusion and exclusion criteria violations for all randomized subjects. Listing 16.2.3 gives analysis populations.

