### 6.5 Physical Examination

Findings from the physical examinations will be summarized through shift tables that, for each system or area examined, compare the normal/abnormal finding at Baseline to the normal/abnormal finding at the Final Visit. Table 14.3.6 gives the results of physical examination. Listing 16.2.11 provides physical examination findings.

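### SAP section 4 keeps unmeasured subjects in the denominator, so by-visit safety percentages fall below the rate among assessed subjects whenever values are missing

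*SAP*

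**What the plan says.** SAP section 4 sets the general tabulation rule: "Categorical (nominal) variables will be summarized using frequency tables (number and percentage of subjects in each category"). It then adds: "If some values are missing, the percentages will sum to less than 100" percent. The matching paragraph in Protocol section 9.7.1 describes the same frequency tables and says nothing about missing values.

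The safety sections of the SAP give no other denominator:

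- Section 6 says only that safety is summarised for the Safety population by treatment received.
- Section 6.2 promises laboratory summaries and shift tables.
- Section 6.4 promises overall ECG findings (Table 14.3.5.1), an ECG shift table (14.3.5.3) and QTcF outlier counts with percentages (14.3.5.4). The outlier counts are given over the whole study and also by scheduled collection or visit.
- Section 6.5 promises tables that "compare the normal/abnormal finding at Baseline to the normal/abnormal finding at the Final Visit".

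The protocol synopsis (Statistical Methods, Safety Analyses, item 9) plans to compare the rate of abnormal physical-examination findings with placebo. The table shells are separate documents (SAP section 10).

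On data collected between visits, SAP section 4 says: "Unscheduled data will be listed and included in the Last Observation Carried Forward (LOCF) analysis". The laboratory shift in Protocol section 9.7.1.4.2 is to "compare the LNH classification at screening to the LNH classification and the Final Visit".

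**The concern.** A population denominator suits adverse-event incidence, where a subject with no report is taken to have had no event. A measured outcome is different. A subject with no ECG at a visit is neither normal nor abnormal, yet under this rule that subject lowers the abnormal percentage exactly as a normal result would.

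Safety is the primary objective, and the safety p-values are descriptive only (SAP section 6), so the printed percentages are what readers will compare. Missing values may also be related to tolerability: SAP section 3.1.2 has subjects who do not tolerate the starting dose leave the study. With about 25 subjects per arm, each unmeasured subject is 4% of the denominator.

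A related gap concerns laboratory data. If an abnormal result comes from an unscheduled on-treatment test and the Final Visit value is normal, no planned laboratory table is told to show it.

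**Working it through.** **Inputs from the documents.** Size: "Approximately 50 subjects (approximately 25 per treatment group) will be randomized in the study" (SAP section 3.2). Dropout, overall only: "assuming a 20% dropout rate, it is anticipated that 40 subjects will complete the study" (Protocol section 7, repeated in 9.2). The documents give no abnormality rate, no missing-data rate and no dropout by arm. Those values are assumptions below.

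**The plan's own figure.** 50 × (1 − 0.20) = 40 completers, as stated. Spread evenly, that is 5 dropouts and 20 completers per arm of 25.

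**What the rule implies.** Let p be the abnormality rate among assessed subjects and m the share of the arm with no value. If the denominator were subjects assessed, the categories would always sum to 100%. A sum below 100% therefore means division by the whole arm:

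- printed rate = p × (1 − m)
- relative shrinkage = m; absolute shortfall = p × m

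**At the planned dropout, equal in both arms, missing values only in dropouts (assumed p = 20%).**

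- No dropout measured, m = 0.20: 0.20 × 0.80 = 16.0%. In counts, 4 of 20 assessed is 20.0%, and 4 of 25 is 16.0%.
- Half of the dropouts measured, m = 0.10: 0.20 × 0.90 = 18.0%.
- All measured, m = 0: no change.

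**If missingness differs by arm (assumed split).** Take 7 of 25 (28%) missing on drug and 3 of 25 (12%) on placebo, which is still 10 of 50 overall.

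| Rate among assessed, drug / placebo | Printed, drug / placebo |
|---|---|
| 20% / 20% | 0.20 × 0.72 = 14.4% / 0.20 × 0.88 = 17.6% |
| 25% / 20% | 0.25 × 0.72 = 18.0% / 0.20 × 0.88 = 17.6% |

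Equal rates print with a gap of 3.2 points. A 5-point excess on drug prints as 0.4 points. With equal rates p from 5% to 30%, the spurious gap is p × (0.28 − 0.12), or 0.8 to 4.8 points. A milder split of 12% against 4% missing, at p = 20%, prints 17.6% against 19.2%. In counts, 4 of 18 and 4 of 22 assessed both print as 16.0% of 25, although the rates among those assessed are 22.2% and 18.2%.

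**Which tables are reached.** Overall ECG findings and the QTcF counts by visit are clearly reached. At Visit 4, a subject who left earlier has no scheduled ECG, and on a plain reading the early-termination ECG does not fill that row. The physical-examination rate compared with placebo is reached. Shift tables are reached only if percentages are printed. The whole-study QTcF count is affected only by subjects with no usable value at all.

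**Unscheduled laboratory values.** SAP section 4 lists unscheduled data and sends them to LOCF. SAP section 5.1.6 defines LOCF for efficacy only. The protocol's laboratory shift uses screening and the Final Visit, and the schedule has only those two laboratory collections. Protocol section 9.4.4.3 allows a repeat of an abnormal test. Read together, these passages name no laboratory summary table that uses an unscheduled result. The QTcF outlier table, by contrast, is stated to cover every assessment in the study.

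**The case against.** **Early-termination data limit the effect.** ECG, laboratory tests and physical examination are due at early discontinuation (Protocol sections 9.1.3 and 9.4.1.4), and SAP section 3.7 asks investigators to make every effort to obtain them. A dropout need not be unmeasured at the end of study. This stands, and it makes the one-fifth shrinkage a ceiling at the planned dropout.

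**The tables are not opaque.** Counts are printed beside percentages, a total below 100% itself signals missing values, and disposition is tabulated by arm. The shells may show the number assessed. This stands in part. The QTcF outlier counts, however, have no complementary category from which the number assessed can be read off.

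**An observed-case denominator can also mislead.** If unmeasured subjects would have had rate q, the full-arm rate is p(1 − m) + qm. The current rule reproduces it only when q = 0, and the proposed one only when q = p. Neither is assured, which is why the number missing must be shown. But q = 0 is the less defensible default for a safety table.

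**Stronger readings that the documents do not support.** A reader might infer that rates will be understated most in the arm with more dropouts. That needs missingness to follow dropout, and no figure by arm is given. Even then it holds only for relative shrinkage: with p = 30% and m = 12% in one arm and p = 10% and m = 28% in the other, the shortfalls are 3.6 and 2.8 points, so the arm with fewer missing values loses more. A reader might also infer that laboratory abnormality rates are affected throughout, but SAP section 6.2 promises shift tables without saying that they carry percentages. Nor are all unscheduled safety values confined to listings: the QTcF outlier table uses them, and a laboratory abnormality may be recorded as an adverse event at the investigator's judgment.

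**Conclusion.** The point holds, conditionally. The SAP's rule divides by the whole arm, and nothing in its safety sections replaces it. Wherever a by-visit value is missing, the printed percentage falls below the rate among those assessed by the relative factor m. At 20% dropout, with missing values only in dropouts and spread evenly over the arms, that is at most one fifth. It is smaller to the extent that early-termination assessments are obtained, and zero if nothing is missing. Missed assessments in completers would add to it.

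Between-arm distortion follows if missingness differs. The 0.8 to 4.8 point range rests on an assumed 28% against 12% split with equal rates in both arms, and says nothing about what this trial will show. No significance level, power or sample size depends on the rule. What is at stake is how descriptive safety tables for the primary objective will be read.

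The unscheduled-data gap holds for laboratory tables only.

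**What to change.** Replace the sentence on missing values in SAP section 4 with:

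> Percentages for measured outcomes by visit use subjects with a non-missing value at that visit (for shifts and changes, also at baseline). The number assessed and the number missing are shown by arm. AE incidence uses the Safety population.

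Carry the same denominators into the table shells for SAP sections 6.2, 6.4 and 6.5.

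In SAP section 6.2, add a laboratory shift from baseline to the worst on-treatment value, scheduled or unscheduled, beside the Final Visit shift.

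The cost is a short SAP edit, some table programming, one extra set of laboratory tables and slightly less favourable abnormality percentages. No data collection changes.

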## 9.4.4.1. Adverse Events

As defined by the ICH Guideline for GCP, an AE is any untoward medical occurrence in a patient or clinical investigation subject administered a pharmaceutical product, which does not necessarily have to have a causal relationship with treatment.

An AE can be:

- Any unfavorable and unintended sign (including an abnormal laboratory finding), symptom, or disease temporally associated with the use of a medicinal product, whether or not considered related to the medicinal product.
- Any new disease or exacerbation of an existing disease.
- Any deterioration in non-protocol-required measurements of laboratory value or other clinical test (e.g., ECG or X-ray) that results in symptoms, a change in treatment, or discontinuation from SM.
- Recurrence of an intermittent medical condition (e.g., headache) not present at baseline.

AEs fall into the categories of "non-serious" and "serious". Surgical procedures are not AEs; they are therapeutic measures for conditions that require surgery. The condition for which the surgery is required is an AE, if it occurs or is detected during the study period.

AEs or SAEs that are ongoing at the subject's last study visit must be followed until resolution or if, in the medical judgment of the Investigator, the event has stabilized or is assessed as chronic.

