### 3. DESIGN OF THE STUDY

### 3.1 STUDY DESIGN

This will be a multicenter, randomized, double-blind, placebo-controlled, parallel group study of the safety and efficacy of SPN-812V in adults with ADHD. The target subjects are male or female adults aged 18 to 64 years, inclusive, with a diagnosis of ADHD. A total of fifty subjects will be enrolled at approximately 5 sites in the US. Subjects will be randomized (1:1) to one of two treatment groups, SPN-812V or placebo.

The study will consist of a Screening Period (within 14 days prior to randomization) and a Dosing Period of 6 weeks. The total subject duration in the study will be up to 8 weeks as illustrated in Figure 1.

[figure not shown]

Figure 1 Study Schematic

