#### 3.4 SCHEDULE OF VISITS AND PROCEDURE

All subjects who are randomized and take any SM will be followed according to the protocol, unless consent for follow-up is withdrawn. The Sponsor, or the Sponsor's designee, must be notified of all deviations from the protocol visits or procedures and these procedures, if applicable, will be rescheduled or performed at the nearest possible time to the original schedule.

The exhibit on the next page presents the schedule of visits and procedures for the study (Table 1).

Table 1. Schedule of Visits and Procedures

Study Phase	Communication Devicts	Dose Treatment Period		End of
	Screening Period	(Visit windo	(Visit window +/- 2 days)	
Activity	Visit 1 Up to 14 Days Prior to Visit 2	Visit 2	Visits 3 – 8	
Informed Consent a	X			
Medical and Psychiatric History and Demographics	X			
Physical Exam	X			X
ECG (12-lead)	X		X c	X
Vital Signs d	X	X	X	X
Hematology	X			X
Urinalysis and drug screen	X			X
CYP2D6 Enzyme Activity Screening	X			
Serum Chemistry	X			X
Serum Pregnancy Test (for FOCP only)	Х			X
Urine Pregnancy Test (for FOCP only)		х		
CAADID	X			
CGI	X	X	X	X
C-SSRS	X	X	X	X
CAARS e		X	X	X
Concomitant Medication	X	X	X	X
Randomization		X		
SM Dispensed		X	X	
SM Diary Dispensed			X f	
Optional SM Administered On-Site g			X	
Optional PK Blood Sampling			X h	
Adverse Events			X	X i

- a To be obtained prior to any study procedures being performed.
- b To be performed at the end of Visit 8 (unless done previously during Visit 8), or at early discontinuation.
- c At Visit 4 only
- d Heart rate, seated blood pressure, temperature, and respiratory rate will be measured at every visit. The vital signs readings will be performed within approximately 10 minutes prior to the scheduled blood draws, where applicable. Height will be taken at screening and weight will be assessed at each visit.
- e CAARS self-report done only at Visits 2 and 8, CAARS investigator-report done at Visits 2-8
- f At Visit 7 to record SM taken prior to Visit 8. Diary to be collected at Visit 8.
- Dose to be administered on-site after the pre-dose draw and an overnight fast at Visit 8; subjects may eat 2 hours after dosing.
- h At Visit 8, subjects who wish to participate will be dosed after an overnight fast and have a series of PK samples drawn. Samples will be taken pre-dose, and at Hours ½, 1, 2, 3, 4, 5, and 6.

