### 5.1.6 Methods for Handling Dropouts or Missing Data

Subjects who discontinue the study without post-randomization scores will not be included in the analysis of efficacy variables. Last observation carried forward (LOCF) technique will be used in the efficacy analysis for subjects who discontinue the study with post-randomization scores where last observation carried forward will be the last non-missing observation on scheduled or unscheduled visits.

If more than one item of a subscale is missing, the score for the subscale (and the total score) will also be considered missing. If only a single item is missing, the mean score for all other items in the subscale will be imputed as the score for the missing item.

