### 6.2 CLINICAL LABORATORY VALUES

Table summaries and by-patient listings of the laboratory test results will be presented. Laboratory testing will be broken down by Hematology, Serum Chemistry, and Urinalysis tests. Tables 14.3.2.1 through 14.3.2.4 will provide summaries for Hematology and Serum Chemistry respectively and associated shift tables. Listings 16.2.8.1 through 16.2.8.6 will provide by-patient listing for hematology, serum chemistry, urinalysis, CYP2D6 enzymes, urine drug test, and urine pregnancy tests respectively.

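### A hematology or chemistry abnormality found at an unscheduled on-treatment draw and normal again at the Final Visit is listed but not counted by arm in the laboratory tables

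*SAP*

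**What the plan says.** SAP 4 says that data are summarized, where appropriate, by protocol-specified visit. It then sets the rule for everything else: "Unscheduled data will be listed and included in the Last Observation Carried Forward (LOCF) analysis". SAP 5.1.6 gives LOCF its only definition: "Last observation carried forward (LOCF) technique will be used in the efficacy analysis for subjects who discontinue the study with post-randomization scores".

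For laboratory data, SAP 6.2 says: "Tables 14.3.2.1 through 14.3.2.4 will provide summaries for Hematology and Serum Chemistry respectively and associated shift tables". It gives no visit basis, no end point for the shift and no rule for worst or unscheduled values. The protocol supplies the first two in section 9.7.1.4.2. On the summaries it says: "By-visit tabular summaries of the laboratory test results will be presented". Its shift tables "compare the LNH classification at screening to the LNH classification and the Final Visit", where the second conjunction evidently means at the Final Visit.

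Table 1 in both documents schedules hematology and chemistry at Visit 1 and End of Study only. Footnote b defines the latter: "To be performed at the end of Visit 8 (unless done previously during Visit 8), or at early discontinuation".

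The ECG section differs. Under SAP 6.4, Table 14.3.5.4 counts by arm the subjects with QTcF outliers over every assessment in the study, as well as by scheduled collection.

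**The concern.** Safety is the primary objective (Protocol 8, SAP 2.1), and the laboratory tables rest on one scheduled post-dose draw. In a subject who stays on treatment, an unscheduled draw is the only possible source of laboratory data before the Final Visit. The stated rule sends such a value to the listings, and the one analysis it may enter is an efficacy method that does not apply to it.

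Whether a transient abnormality reaches any by-arm count then depends on whether it is recorded as an adverse event, which SAP 3.6.2 leaves to the Investigator's judgment. A QTcF outlier needs no such step. What is at stake is a complete between-arm count of laboratory abnormalities. Without it, a reader has to build the count from Listings 16.2.8.1 and 16.2.8.2.

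**Working it through.** The plan states no figure to reproduce, so the check traces one value through the text and then adds scale.

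**Trace.** Take a continuing subject with a chemistry value that is normal (N) at screening, high (H) at an unscheduled draw after first dose, and N at the Final Visit.

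1. By-visit summary (SAP 4, Protocol 9.7.1.4.2): the unscheduled draw belongs to no protocol-specified visit, so it enters no row.
2. Shift table (Protocol 9.7.1.4.2): only screening and the Final Visit are compared, so the subject counts as N to N.
3. LOCF (SAP 5.1.6): efficacy only, so not applicable.
4. Listings (SAP 4, SAP 6.2): the value is shown.
5. AE tables (SAP 6.1.1, Tables 14.3.1.1.1 to 14.3.1.1.4): counted by arm if reported as an adverse event.

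The subject adds 0 to the count of post-dose high values in Tables 14.3.2.1 to 14.3.2.4. A QTcF outlier following the same course would be counted once in Table 14.3.5.4.

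**What falls outside the gap.** A draw at early discontinuation is an End of Study assessment (Table 1, footnote b) and is tabulated. A pre-dose repeat may serve as baseline under SAP 5.1.1. That is a further use of unscheduled data, but not an on-treatment one.

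**Schedule.** SAP 3.1: "The study will consist of a Screening Period (within 14 days prior to randomization) and a Dosing Period of 6 weeks". From Table 1:

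- Hematology and chemistry: Visit 1 and End of Study, so 1 scheduled post-dose time point.
- ECG: Visit 1, Visit 4 and End of Study, so 2 scheduled post-dose time points.
- Longest interval between the two scheduled laboratory draws: 14 + 6 × 7 = 56 days, with a visit window of +/- 2 days.

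**Scale of one subject** (not an estimated effect):

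- Randomized arm of about 25 (SAP 3.2): 1/25 = 4 percentage points.
- Anticipated completers (Protocol 9.2, 20% dropout): 50 × (1 − 0.20) = 40. If dropout is equal between arms, which is an assumption, that is 20 per arm, and 1/20 = 5 percentage points.

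The documents give no number of unscheduled laboratory results, and it may be zero.

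**The case against.** The strongest reply is that the documents hardly produce this case and already cover the part that matters clinically.

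- **Few such draws.** Protocol 9.1.1 allows a repeat of an abnormal result during screening. Protocol 9.4.4.3 allows one confirmatory repeat. Table 1 footnote i attaches follow-up of abnormal values to the End of Study adverse event cell. These mostly follow a scheduled draw, so they fall before dosing or at or after the Final Visit. Protocol 9.4.4.6 expressly allows extra ECGs, but the laboratory section has no parallel sentence. This stands: the gap needs a for-cause draw during dosing, which is neither forbidden nor foreseen in so many words.
- **The AE route.** The first item of the AE definition in Protocol 9.4.4.1 covers "Any unfavorable and unintended sign (including an abnormal laboratory finding), symptom, or disease temporally associated with the use of a medicinal product". The third covers a worsening in a test the protocol did not require, if it leads to symptoms, changed treatment or stopping study medication. A consequential unscheduled abnormality is therefore an adverse event, counted by arm by system organ class, preferred term, relationship and severity. This also stands, and it confines the gap mainly to abnormalities not reported as AEs.
- **Unseen shells.** SAP 6.2 is silent on the visit basis, SAP 4 qualifies its by-visit rule, and the shells are separate documents (SAP 10). They could already provide for worst values. This limits certainty, but it does not put the rule into the SAP.
- **Duplication and bias.** For a subject without an unscheduled draw, the worst post-dose value is the Final Visit value, so an added table would largely repeat the existing one. Where the two differ, it mixes for-cause with scheduled tests. Both points are fair. They argue for showing the versions side by side, not for leaving the count out.

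A reader might infer that transient laboratory abnormalities disappear from the safety report. The documents do not support that: every value is listed, and the consequential ones reach the AE tables.

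**Conclusion.** As written, SAP 4 and 5.1.6 with Protocol 9.7.1.4.2 leave an unscheduled post-first-dose hematology or chemistry abnormality out of the by-arm laboratory tables if it is normal at the Final Visit. SAP 6.4 takes the fuller approach for QTcF outliers, and no reason is given for the difference. The gap lies only in the arm-level laboratory summary. No listing, AE count or efficacy result changes.

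The conclusion assumes that the laboratory tables follow the protocol's visit basis and that the shells add nothing to it. Each affected subject would be 4 to 5 percentage points of an arm, but there may be few such subjects or none.

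Two stronger readings should be resisted. The interval of up to 56 days between scheduled draws describes the visit schedule. It is not a result of the unscheduled-data rule, and the proposed table would add no draw. Nor is there a demonstrated ECG gap: Table 14.3.5.4 already covers QTcF outliers, and Table 14.3.5.3 merely does not say whether unscheduled post-dose ECGs count. This is a cheap improvement of low priority.

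**What to change.** In SAP 6.2, add a by-arm hematology and chemistry shift table from the last pre-dose value to the worst post-first-dose value, using scheduled and unscheduled results. Give any-low and any-high their own columns, because one subject can have both. Place it beside the scheduled-only shift table, and report the number of subjects per arm with any unscheduled test. Amend the SAP 4 sentence on unscheduled data to name this use.

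For ECG, at most add one sentence to SAP 6.4 saying that the overall-finding shift in Table 14.3.5.3 includes unscheduled post-dose ECGs.

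The cost is SAP wording and one added laboratory table from data already collected, with no change to study conduct. The downside is that for-cause testing may differ between arms, so the worst-value and scheduled-only versions must be read together. If the shells already provide this, the SAP wording alone is enough.
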